5.4.5.2. Azacitidine

For azacitidine dose modification, refer to the local package insert (or SPC) or Investigational Product Manual.

5.5. Drug Storage

The investigator, or an approved representative, eg, pharmacist will ensure that all investigational products, including any comparative agents and/or marketed products are stored in a secured area with controlled access under recommended storage conditions and in accordance with applicable site and regulatory requirements.

Storage conditions stated in the SRSD (IB for glasdegib and EU SPC for Vidaza®²⁷) will be superseded by the storage conditions stated in the labeling.

Glasdegib should be stored as described on the drug label. Note that the storage conditions in any study documentation will be superseded by the storage conditions stated on the product label. Patients should be instructed to keep their medication in its original container. Returned medication should be stored at the clinical site separately from medication that needs to be dispensed.

Azacitidine will be stored according to the labeled storage conditions.

Investigators and site staff are reminded to check temperatures daily (ie, manually or by using alarm systems to alert of any excursions) and ensure that thermometers are working correctly as required for proper storage of investigational products. These include thermometers for both the room storage and refrigerator storage. Any temperature excursions should be reported to the sponsor.

The investigational product(s) must be stored as indicated. Deviations from the storage requirements, including any actions taken, must be documented and reported to the sponsor. Once a deviation is identified, the investigational product must be quarantined and not used until the sponsor provides documentation of permission to use the investigational product.

Site systems must be capable of measuring and documenting (for example, via a log), at a minimum, daily minimum and maximum temperatures for all site storage locations (as applicable, including frozen, refrigerated and/or room temperature products). This should be captured from the time of investigational product receipt throughout study. Even for continuous monitoring systems, a log or site procedure which ensures active daily evaluation for excursions should be available. The operation of the temperature monitoring device and storage unit (for example, refrigerator), as applicable, should be regularly inspected to ensure it is maintained in working order.

Any excursions from the product label storage conditions should be reported upon discovery. The site should actively pursue options for returning the product to labeled storage conditions, as soon as possible. Deviations from the storage requirements, including any actions taken, must be documented and reported to the sponsor.

Once a temperature excursion is identified, the investigational product must be quarantined and not used until the sponsor provides documentation of permission to use the investigational product. Specific details regarding information the site should report for each excursion will be provided to the site.

Site staff will instruct patients on the storage requirements for take home medications including how to report temperature excursions.

5.6. Drug Accountability

The investigator's site must maintain adequate records documenting the receipt, use, loss, or other disposition of the drug supplies. At each dispensing visit (Cycle 2 Day 1, Cycle 3 Day 1, etc. or when there is a dose reduction), all unused or partially used bottles must be returned by patients to the Investigator. The number of tablets returned by the patient at the end of the cycle will be counted, documented and recorded.

The sponsor or designee will provide guidance on the destruction of unused investigational product (eg, at the site). If destruction is authorized to take place at the study site, the investigator must ensure that the materials are destroyed in compliance with applicable environmental regulations, institutional policy, and any special instructions provided by sponsor or designee and all destruction must be adequately documented.

5.7. Concomitant Treatment(s)

All concomitant medications and treatments must be recorded in the CRF. Any prior treatment received within 28 days prior to study entry (including hematopoietic growth factor receptor agonists: erythropoietin, granulocyte colony stimulating factor (G-CSF), romiplostim, eltrombopag) will be recorded in the CRF.

In addition, any transfusion (red blood cells or platelets) within 8 weeks prior to screening should be recorded in the CRF.

All prior immunosuppressive therapy (eg, cyclosporine) used to treat MDS, or all prior cyto-reduction therapy (eg, hydroxyurea) used to treat AML or CMML, will be recorded regardless of when they were received by the patient. Information collected will include dates of use, best treatment response and the reasons for stopping therapy.

Every concomitant treatment, blood products, growth factors, as well as interventions, required by the patients during the active study treatment (and up to 28 days following last study drug administration or until initiation of another anti-cancer treatment) and the reason for its administration must be recorded on the CRF.

All concomitant medications the patient is currently receiving must be reviewed by the Sponsor prior to enrollment in the safety LIC. Study entry criteria are defined in [Section 4](#).

5.7.1. Restricted or Prohibited Concomitant Medications

The following medications are not allowed during the active study treatment period:

- Agents used to treat AML or MDS; for control of rapidly progressing leukemia, hydroxyurea and/or leukopheresis may be used before and for up to 1 week after the first dose of glasdegib;
- Investigational agents;

- CYP3A4/5 Inducers: A drug-drug interaction study in healthy subjects with the strong CYP3A4 inducer, rifampin, resulted in a 70% decrease in plasma exposures (AUC_{inf}) and a 35% decrease in peak plasma concentration (C_{max}) of a single 100-mg oral dose of glasdegib. Therefore co-administration of glasdegib and moderate/strong CYP3A4/5 inducers is not permitted. A comprehensive list of moderate/strong CYP3A4/5 inducers is provided in [Appendix 4](#). However, if you are uncertain whether a concomitant medication is contraindicated, you should contact the Sponsor study team.

The following medications have use restrictions during the active study treatment period:

- CYP3A4/5 Inhibitors: In vitro studies with human liver microsomes and recombinant CYP enzymes indicated that glasdegib metabolism is primarily mediated by the drug-metabolizing enzyme CYP3A4/5. Clinically, there is likelihood that glasdegib plasma concentrations may be increased in the presence of co-administered inhibitors of the CYP3A4/5 enzymes. In a healthy volunteer study, ketoconazole, a potent CYP3A4/5 inhibitor, produced a 2.4-fold increase in plasma exposure and a 1.4-fold increase in peak plasma concentration of glasdegib. Therefore a potential exists for drug-drug interactions with CYP3A4/5 inhibitors, and co-administration of glasdegib in combination with moderate/strong CYP3A4/5 inhibitors is not recommended. Selection of concomitant medication with no or minimal CYP3A4/5 inhibition potential is recommended. Moderate/strong CYP3A4/5 inhibitors ([Appendix 6](#) and [Appendix 7](#)) should be used with caution and only if considered medically necessary. If a moderate/strong CYP3A4/5 inhibitor is to be initiated in addition to glasdegib, the guidance provided in [Section 7.6](#) and dose modifications for QT prolongation per [Table 14](#) must be followed.
- Drugs with a known risk of Torsade de pointes (TdP): Glasdegib has been shown to have the potential to prolong the QTc interval in pre-clinical studies and at doses >200 mg (see [Section 1.2.20](#) for summary of TQT study). While the glasdegib dose being evaluated in this study is 100 mg, the concomitant administration of glasdegib and drugs with a known risk of Torsade de pointes should be avoided whenever possible. A list of such drugs is provided in [Appendix 5](#). Use of these drugs is not recommended unless there are no alternatives. If a TdP drug is to be initiated in addition to glasdegib, the guidance provided in [Section 7.6](#) and dose modifications for QT prolongation per [Table 14](#) must be followed.
- QT prolonging medications (without a risk of TdP) should be avoided whenever possible.
- Concomitant administration of multiple moderate/strong CYP3A4/5 inhibitors, TdP drugs, and/or QT prolonging medications (without a risk of TdP) is not recommended and must be discussed with the Sponsor Medical Monitor.

5.7.2. Permitted Concomitant Medications

5.7.2.1. Best Supportive Therapy

Best Supportive Therapy (BST) administration is permitted according to Institutional guidelines for all patients on study. BST will be provided by the site and may vary depending on the patient's signs and symptoms, site current practice, and country practice. It includes medications and supportive measures that may palliate disease-related symptoms, improve quality of life and treat bacterial, fungal or viral infections. BST may include:

- Blood transfusions;
- Platelet transfusions;
- Antibiotics;
- Anti-fungal agents;
- Anti-viral agents.

5.7.2.2. Hematopoietic Growth Factors

Hematopoietic growth factors (eg, G-CSF, GM-CSF) may be used according to local practice and guidelines.

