4.2. Exclusion Criteria

4.2.1. Safety Lead-in Cohort

The safety lead-in cohort has been completed.

Patients with any of the following may not be included in the study:

1. Patients with AML who are candidates for standard induction chemotherapy as first line treatment.
2. Therapy-related (secondary to radiation or chemotherapy) MDS or AML.
3. Prior hypomethylating agents or cytotoxic chemotherapy for MDS, AML or CMML (prior immunosuppressive therapy and hydroxyurea are permitted provided that treatment is stopped within 8 and 2 weeks from study entry, respectively).
4. Previous hematopoietic stem cell transplant.
5. Prior treatment with a licensed or experimental smoothed inhibitor (SMOi) and/or hypomethylating agent (HMA).
6. Participation in a clinical study involving an investigational drug(s) (Phases 1-4) within 4 weeks prior to study entry.
7. Major surgery or radiation within 12 weeks prior to study entry.
8. Patients known to be refractory to platelet or packed red cell transfusions as per institutional guidelines, or who are known to refuse or who are likely to refuse blood product support.

9. Treatment with hematopoietic growth factors including: erythropoietin, granulocyte colony stimulating factor (G-CSF), and granulocyte macrophage colony stimulating factor (GM-CSF), or thrombopoietin receptor agonists within 3 weeks prior to study entry.
10. Any ongoing medical condition requiring chronic use of moderate to high dose steroids (defined as ≥ 10 mg/day of prednisone or equipotent dose of another corticosteroid).
11. Any anti-cancer treatment within 2 weeks prior to study entry.
12. Current use or anticipated requirement for drugs that are known strong CYP3A4/5 inducers ([Appendix 4](#)).
13. Diagnosis of any malignant disease other than MDS, AML or CMML within the prior 12 months, with the exception of adequately treated: (i) in-situ carcinomas, (ii) basal or squamous cell carcinoma, or (iii) non-melanoma skin cancer.
14. Known malabsorption syndrome or other condition that may impair the absorption of the study drug (eg, gastrectomy, lap band, Crohn's disease) and inability or unwillingness to swallow tablets or capsules.
15. Patients with active, uncontrolled bacterial, fungal or viral infection, including hepatitis B (HBV), hepatitis C (HCV), known human immunodeficiency virus (HIV), or acquired immunodeficiency syndrome (AIDS) related illness.
16. Known uncontrolled central nervous system (CNS) involvement.

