6.1.2.1.2. MDS Cohort

Hematologic Responses

- CR
- PR,
- marrow CR (mCR)
- SD
- Complete or Partial Cytogenetic Response

Hematologic Improvement (HI):

HI (defined only for MDS patients) is derived based on hematology lab and RBC transfusion data according to criteria detailed in Appendix 2.

Of note that HI for neutrophils improvement obtained within 3 weeks of the last administration of growth factors (GCSF/GM-CSF) is considered not evaluable. Additionally, HI for erythroid improvement obtained within one week of the last administration of transfusion of red blood cell is considered not evaluable, and HI for platelets improvement obtained within 3 days of the last administration of transfusion of platelets is considered not evaluable.

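### Hematologic improvement in the MDS cohort is screened for growth factors in the neutrophil lineage only; erythroid and platelet improvement under a stimulating agent started or increased on study would be counted

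*Protocol*

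**What the plan says.** **Permission on treatment.** Protocol 5.7.2.2 reads: "Hematopoietic growth factors (eg, G-CSF, GM-CSF) may be used according to local practice and guidelines". The two named agents are examples, and no agent is excluded.

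**Scope of the class.** Protocol 5.7, on recording treatment received in the 28 days before entry, lists "hematopoietic growth factor receptor agonists: erythropoietin, granulocyte colony stimulating factor (G-CSF), romiplostim, eltrombopag". Lead-in exclusion 9 (Protocol 4.2.1) opens with "Treatment with hematopoietic growth factors including: erythropoietin, granulocyte colony stimulating factor (G-CSF" and ends with "or thrombopoietin receptor agonists within 3 weeks prior to study entry". The expansion exclusions (Protocol 4.2.2) contain no corresponding criterion.

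**Possible counter-text.** Protocol 5.7.1 bars drugs given as treatment for AML or MDS during active study treatment. It names neither erythropoietin nor thrombopoietin-receptor agonists.

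**The HI screens.** SAP 6.1.2.1.2 has three:
- neutrophils: "HI for neutrophils improvement obtained within 3 weeks of the last administration of growth factors (GCSF/GM-CSF) is considered not evaluable"
- erythroid: "HI for erythroid improvement obtained within one week of the last administration of transfusion of red blood cell is considered not evaluable"
- platelets: "HI for platelets improvement obtained within 3 days of the last administration of transfusion of platelets is considered not evaluable"

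**Derivation and reporting.** HI is derived from hematology laboratory and red-cell transfusion data against the criteria in Appendix 2 of either document, and it must last at least 8 weeks. SAP 8.2.2.2.2 reports, on the full analysis set, the share of the MDS cohort that ever reaches HI, with an exact 95% interval. Protocol 5.7 requires on-treatment growth factors to be recorded on the CRF.

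**The concern.** The SAP already accepts that a neutrophil rise close to G-CSF or GM-CSF should not count as HI. The same reasoning applies to hemoglobin under erythropoietin and to platelets under a thrombopoietin-receptor agonist, but the rule stops at one of the three lineages. The transfusion screens do not fill the gap. They remove counts inflated by a recent transfusion, not counts raised by a drug.

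Erythroid HI can also be met by a fall of at least 4 red-cell transfusions per 8 weeks. An agent that lowers transfusion need can satisfy that route, and a one-week transfusion window cannot detect it.

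HI is a named secondary endpoint of the MDS cohort (Protocol 2.4). The cohort has no control arm sharing the co-medication, so the gap can only raise the reported rate.

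**Working it through.** **Step 1. Set the texts side by side.**

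| Lineage | HI threshold (Appendix 2) | Transfusion screen (SAP 6.1.2.1.2) | Growth-factor screen (SAP 6.1.2.1.2) |
|---|---|---|---|
| Neutrophil | at least doubled, and up by more than 0.5 x 10^9/L | none | 3 weeks from G-CSF/GM-CSF |
| Erythroid | Hgb up by at least 1.5 g/dL, or at least 4 fewer red-cell transfusions per 8 weeks | 1 week from red cells | none |
| Platelet | up by at least 30 x 10^9/L from above 20 x 10^9/L, or from below to above 20 x 10^9/L and at least doubled | 3 days from platelets | none |

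Nothing in Appendix 2 closes the two open cells. Pretreatment counts must be free of transfusion influence, but growth factors are not mentioned. The qualifier about there being no other explanation applies to progression or relapse after HI, not to HI itself.

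**Step 2. Who is exposed.** Pretreatment values are averages of at least two measurements at least a week apart. A patient on a stable agent at entry already carries its effect in the baseline. Together with the 8-week duration, this confines the problem mainly to patients who start or intensify an agent on study.

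**Step 3. Reproduce the plan's precision figure.** Protocol 9.1.2 gives a maximum exact 95% interval width of 0.374 at n = 30. It is stated for CR, but HI uses the same exact method and analysis set. The Clopper-Pearson interval is widest at 15/30: 0.6870 − 0.3130 = 0.3740 from these rounded limits (0.3741 unrounded), which agrees.

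**Step 4. Effect per patient.** 1/30 = 3.3 percentage points. For example, if the properly screened result were 13/30 = 43.3% (95% CI 25.5 to 62.6), two misattributed patients would make it 15/30 = 50.0% (31.3 to 68.7).

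**Step 5. Illustration under assumed inputs.** The documents give no usage or response rates for these agents. Let p be the HI rate without the agent, u the share of the remaining patients given one, and r the share of those who then reach and hold an HI threshold. A patient who reaches HI anyway in any lineage cannot be newly misclassified, so

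overstatement = (1 − p) × u × r.

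Assume p = 0.30 to 0.49, where the upper value is the azacitidine-arm HI rate quoted in Protocol 1.2.16.1 (87/177), u = 0.10 to 0.30 and r = 0.20 to 0.40.
- Low: 0.51 × 0.10 × 0.20 = 0.0102, about 1 point (0.3 patients of 30).
- High: 0.70 × 0.30 × 0.40 = 0.084, about 8 points (2.5 patients of 30).

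This range shows scale only. It is not an estimate for this trial.

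**The case against.** The strongest reply is that on-study use of these agents is inferred. Protocol 5.7.2.2 names only G-CSF and GM-CSF, and 5.7.1 bars drugs used to treat the disease, which a site might take to cover erythropoietin. The list in Protocol 5.7 concerns pre-entry treatment and uses a slightly different term. Exclusion 9 puts thrombopoietin-receptor agonists after a separate conjunction, which sets them apart from the growth factors it lists.

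Much of this stands. The platelet part is weaker than the erythroid part, and the two protocol sections need reconciling. It does not remove the gap: the 5.7.2.2 permission is open-ended, exclusion 9 names erythropoietin as a growth factor, and even if 5.7.1 were read as a ban, the SAP has no rule removing HI obtained under a barred agent.

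It is also fair that HI is a descriptive rate with no formal hypothesis (SAP 4.1). At n = 30 the exact interval can reach about 18.7 points either side (0.374/2), so one or two patients lie well within sampling error. That limits the importance. But the shift runs in one direction only, and the interval does not allow for it.

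Three stronger readings do not hold.
- A reader might infer that the plan credits these rises to study treatment. It does not: it reports how many patients ever reach HI, with no causal contrast and no planned comparison with a historical HI rate.
- A reader might infer that the primary result is affected through this rule. The HI screens do not govern CR, and the futility rule uses CR only.
- A reader might take lead-in exclusion 9 as support for a 3-week evaluability window. It is a pre-entry washout in a completed cohort.

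**Conclusion.** The gap is real and limited. As written, the HI derivation would count an erythroid improvement obtained under erythropoietin started or increased after baseline, provided it meets the threshold and lasts at least 8 weeks. It would do the same for platelets under a thrombopoietin-receptor agonist, if such agents are in fact used.

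The certain part of the size is 3.3 points per misattributed patient at n = 30. The number of such patients cannot be derived from the documents. The 1 to 8 point illustration rests wholly on assumed usage and response, and no larger claim is supported. The effect is confined to one descriptive secondary endpoint of the MDS cohort. Because it is a stated derivation rule that can bias that endpoint upward, and is easily repaired, it should be settled before the final analysis.

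**What to change.** In SAP 6.1.2.1.2 and 8.2.2.2.2, pre-specify from the CRF growth-factor records that erythroid HI obtained under an erythropoiesis-stimulating agent, and platelet HI obtained under a thrombopoietin-receptor agonist, is not counted when the agent was started or increased after baseline. At minimum, make this a pre-specified sensitivity analysis reporting the HI rate with and without these cases. For erythroid HI, state that the rule covers the transfusion-reduction route as well as the hemoglobin route.

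The sponsor should set the time window. Three weeks would match the SAP's existing neutrophil rule, but that rule needs checking first. The SAP was finalized after Amendments 5 and 6, and Amendment 7 then removed the 3-week G-CSF/GM-CSF timing requirement for disease assessments, listing Protocol 9.3.6 among the affected sections.

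Separately, reconcile Protocol 5.7.1 and 5.7.2.2 so that sites and analysts know whether these agents are allowed on treatment.

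**Cost.** SAP wording, one derivation step and one extra table line on data already collected, plus a protocol clarification. The downside is that some genuine improvements in users of these agents would not be counted, because SAP 7.2 treats patients not known to have responded as non-responders. Reporting the rate both ways makes that trade-off visible.

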5.7.2.3. Anti-Emetic and Anti-Diarrheal Therapy

Patients should be pre-medicated with anti-emetics for nausea and vomiting before each dose of azacitidine in all cycles according to local practice and guidelines.

Primary prophylaxis of diarrhea is permitted at the Investigator's discretion. The choice of the prophylactic drug is up to the investigator assuming the drug is not contraindicated as described in [Section 5.7.1](#).

5.7.3. Surgery

Caution is advised on theoretical grounds for any surgical procedures during the study. The appropriate interval of time between surgery and glasdegib required to minimize the risk of impaired wound healing and bleeding has not been determined. Stopping glasdegib is recommended at least 7 days prior to surgery. Post-operatively, the decision to reinstitute glasdegib treatment is up to the Investigator with Sponsor approval and should be based on a clinical assessment of satisfactory wound healing and recovery from surgery.

6. STUDY PROCEDURES

6.1. Screening

Screening can be accomplished over one or multiple visits over a 4-week period (28 days), unless specifically noted otherwise (ie, bone marrow sample collection). Protocol specific tests or procedures not considered standard of care can only be done after the patient has signed the Informed Consent document. The Informed Consent document may be signed up to 60 days prior to study entry.

See the [Schedule of Activities for the Safety Lead-in](#) and the [Schedule of Activities for the Expansion: MDS and AML Patients](#) for a complete list of assessments and procedures to be collected during the screening visit.

6.2. Study Period

See the [Schedule of Activities for the Safety Lead-in](#) and the [Schedule of Activities for the Expansion: MDS and AML Patients](#) for a detailed list of the assessments and procedures to be collected. Study entry is defined as when the patient is enrolled into the IRT system. Patients must be enrolled into the IRT system prior to receiving first dose of study drug.

All assessments on Cycle 1 Day 1 should be collected pre-dose, unless documented otherwise.

